Quality Assurance: For each session, TAs will fill out a quality assurance form to assess the extent to which key elements and activities from the program manual were covered. We will record each session, and independent raters on the SA team will code the extent to which key elements were covered; $\kappa \geq .70$ will indicate adequate consistency between coders.

Curriculum Revision: The curriculum development team (Drs. [name], [name], and [name]) will thoroughly review and discuss results with the Community Advisory Board annually. These discussions will help us to optimize our pilot randomized controlled trial.

Survey Measures: We will draw on our formative South African research and community input to adapt measures. We will provide surveys in English and Xhosa. Pilot data will allow us to gain valuable information about psychometric properties of the proposed scales in both languages.

Data Analysis Plan (Open pilot): Data from the small pre-pilot sample ($N=10$) will be analyzed and will be primarily used to inform ongoing modifications to the TAP intervention to maximize acceptability and retention. Baseline and follow-up quantitative data will be examined for within-group trends in ART initiation.

RCT - Randomization. Participants will be identified from those in previous studies who gave permission to be contacted for future research, through links with the Community Advisory Board or at the VCT rooms of 4 local clinics, where we will also review daily testing logs and treatment logs, and will contact those found to be eligible and not starting ART within 3 months of testing. Those who then go on to meet eligibility criteria will be selected to enroll and asked to complete a baseline questionnaire. HIV testing itself is not part of this study.

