We will use a blocked randomization design based on gender, with a goal of equal representation of males and females. Participants will be randomized to the standard of care (referral to initiate ART) or the intervention arm. A computerized random-number generator will be used to formulate an allocation schedule; participants will be given their assigned allocations within sealed opaque envelopes. The RA enrolling patients will be blinded to the randomization assignment. Upon completion of the baseline questionnaire, the randomization assignment will be revealed. For participants randomized to the TAP arm, the RA will notify the TA, who will come to meet the participant immediately upon completion of the survey. We will seek to prevent control group contamination (i.e., controls being influenced by what the intervention group is learning). For contamination to threaten the ability to detect intervention effects, statistical models suggest that $\geq 30\%$ of the control group must receive the equivalent of a full-strength intervention², which we believe to be highly unlikely. Nevertheless, we will survey participants about possible contamination (e.g., whether they discussed this study with community members) upon study completion.

Data collection.

Primary Outcome. ART initiation – Assessed at the completion of the intervention (month 3) and monthly through 6 months post-intervention. This will be measured through both self-report, medical records at GCHC, and accessing data through the NHLS.

Demographics. We will collect baseline demographic data, and HIV clinical data (diagnosis date, clinical history, most recent CD4 count).

Laboratory testing. Standard protocol at the testing center is testing of the participant's blood to determine HIV status and CD4 and participant eligibility. This is done routinely already at GCHC.

Self-Report Measures. We will administer two sets of surveys to the pilot groups (baseline and at completion of the intervention) to test survey questions and tracking procedures. Our current

study in Gugulethu utilizes an interviewer-administered survey that has been shown to be feasible. Participants will complete the baseline survey before randomization. Code numbers will link data over time. Intervention participants who drop out of the program will be encouraged to complete all surveys.

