Primary data analysis will be an intent-to-treat analysis, which includes all randomized participants. Of note, every attempt will be made to continue assessing participants even if they drop out of treatment. In addition, we will replicate all analyses with the completers only. The hypothesis that The Treatment Ambassador Program will yield higher rates of ART initiation by the completion of the intervention will be tested using Fisher's exact test; the treatment effect estimate will be summarized in terms of a relative risk and 95% confidence interval. Any baseline demographic or clinical variables identified as necessary covariates in preliminary analyses will be included in a logistic regression analysis that examines the main effect of treatment condition on the rates of ART initiation.

Power/Sample Size Considerations. Because this is a pilot study, power considerations for testing null hypotheses are somewhat less relevant than having adequate degrees of freedom to estimate treatment effects with a reasonable degree of precision for potential use in a future fully-powered trial. However, for completeness, we present a summary of the power analyses for the primary hypothesis below. With a sample size of up to 45 per treatment group, the probability is greater than 80 percent that the study will detect a difference of 25% in the percent who initiate ART. This is based on the assumption that the percent who initiate ART in the control group is approximately 10%, as seen in our prior research in SA. Thus, the study is adequately powered to detect medium-to-large effect sizes (corresponding to a relative risk = 3.5) for the primary outcome. Finally, allowing for a dropout or attrition rate anticipated to not be greater than 10%, we plan to recruit a total of up to 90 participants (45 per group) to ultimately guarantee our complete sample of 80 participants. This proposed sample size provides more than sufficient degrees of freedom to obtain a precise estimate of the primary outcome event rate and a preliminary relative risk

comparison of the two treatment groups, even when allowing for up to 10% loss to follow-up. If promising results are detected, these data will provide an estimate of the reliability of the intervention effect to inform power calculations for a larger RCT.

Process Evaluation to Examine the Feasibility and Acceptability of the Intervention.

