Process evaluation analysis. We will use an inductive content analytic approach to analyze qualitative data. This approach consists of the following steps: (1) data reduction through coding, (2) category construction, (3) comparison, and (4) interpretation.

Coding. Coding will begin with a provisional start-list of themes based on prior research. Twenty percent of the interviews will be independently read and new themes iteratively generated based on identifying themes not present in the start-list, which will result in a codebook. The team members will code 20% additional interviews to calibrate the methods of evaluation, and one individual, using the standards established, will code the remaining interviews (Cohen's Kappa ≥ 0.80). For each of the seven survey measures, we will compare responses at 6 months by computing the mean response for each arm, a 95% bootstrap confidence interval for the between-arm difference in means, and a permutation test p-value for the between-arm difference in means adjusted for each participant's baseline score. To assess preliminary efficacy, rates of ART initiation at 3 months for the two arms will be

compared by computing the relative “risk” of initiation and testing for an association between arm and initiation rate using Fisher’s exact test.

We will use NVivo10[©] (QSR International Pty Ltd 2014) software to code and manage the data. The result will be a reduced data set consisting of an initial set of concepts and corresponding sections of interview/field note text -- the basis for category construction. Categories will be developed by grouping codes and coded data into meaningful clusters to form larger concepts. We will formulate labels and definitions for each new concept. Final versions of categories will include: (1) the category label or name, which should convey a category’s essential meaning; (2) the operational definition and/or an indication of the variety of specific forms the category takes; and (3) evidence of validity in the form of examples of the data from which the category was formulated. The role of interpretation here is to develop conceptual categories into larger explanations to guide process evaluations.

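### As worded, each 6-month survey measure gets an unadjusted bootstrap interval beside a baseline-adjusted permutation p-value; taking both from one adjusted difference is a small gain at no cost

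*Combined protocol and SAP*

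**What the plan says.** The analysis of the survey measures is one sentence in the Coding paragraph under Process evaluation analysis. It opens: "For each of the seven survey measures, we will compare responses at 6 months by computing the mean response for each arm". It then adds "a 95% bootstrap confidence interval for the between-arm difference in means, and a permutation test p-value for the between-arm difference in means adjusted for" the participant's own baseline score. The between-arm difference is named twice, and the baseline adjustment follows only the second mention.

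The baseline score precedes allocation. The Self-Report Measures paragraph of the RCT section states: "Participants will complete the baseline survey before randomization".

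No other section extends the adjustment to the interval. The covariate rule is triggered by significant baseline imbalance in strong predictors of ART initiation, and it leads to a model for that outcome: "Any baseline demographic or clinical variables identified as necessary covariates in preliminary analyses will be included in a logistic regression analysis". No adjusted estimate or adjusted interval for the survey measures is specified anywhere.

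**The concern.** On the literal reading, the interval and the p-value printed side by side for a measure rest on two different estimates: the raw difference and the baseline-adjusted difference. Under randomization both estimate the same population quantity, so neither is biased. Two things are lost:

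- **Precision.** The interval is wider than it needs to be whenever baseline and 6-month scores correlate. The Power/Sample Size paragraph says that in this pilot precise estimation matters more than testing, yet it is the interval that omits the baseline score.
- **Coherence.** A reader can meet an interval that spans zero beside a small p-value, or the reverse, with no explanation in the plan.

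The sentence also leaves room for either interval. An analyst could defend producing the adjusted or the unadjusted one after seeing the data.

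**Working it through.** **Inputs from the documents.** Seven measures at 6 months, with a 95% interval (Coding paragraph). 1:1 allocation (Recruitment Procedures). Up to 45 per arm are recruited "to ultimately guarantee our complete sample of 80 participants", hence 40 per arm.

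**Assumptions.** The documents give neither r nor an effect size d (in SD units) for these measures. The Survey Measures section treats the behaviour of the scales as something to be learned: "Pilot data will allow us to gain valuable information about psychometric properties of the proposed scales in both languages". I therefore use r from 0 to 0.7 and d from 0 to 1.0. The plan does not name its adjustment method; I take it to be ANCOVA on the baseline score. Scores are bivariate normal unless stated.

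**Plan's own figure.** There is none for the survey measures. The stated power of more than 80% concerns ART initiation and is not used here.

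**Step 1: interval width.** The ratio of unadjusted to adjusted standard error is 1/√(1 − r²). The unadjusted 95% half-width is 1.96 × √(2/40) = 0.438 SD; multiplying by √(1 − r²) gives the adjusted one.

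| r | SE ratio | Simulated bootstrap width ratio | Adjusted half-width (SD) |
|---|---|---|---|
| 0 | 1.000 | 0.99 | 0.438 |
| 0.3 | 1.048 | 1.04 | 0.418 |
| 0.5 | 1.155 | 1.15 | 0.380 |
| 0.7 | 1.400 | 1.39 | 0.313 |

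At r = 0, adjusting costs one degree of freedom, about 0.6% in width. On simulated skewed 1–5 scores with observed r of 0.25, 0.42 and 0.62, the unadjusted interval is 3%, 10% and 27% wider.

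**Step 2: gap between the two estimates.** The SD of (raw minus adjusted) is r × √(2/40), which is 0.067, 0.112 and 0.157 SD at r = 0.3, 0.5 and 0.7.

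**Step 3: how often the two outputs point different ways.** The comparison is interval excluding 0 against p ≤ 0.05. This is a common reading convention; the plan sets no such rule. There were 2,000 simulated trials per setting, 40 per arm, with 599 within-arm percentile-bootstrap resamples and 599 permutations of the ANCOVA difference. Entries are percentages of trials.

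| r | d = 0 | 0.2 | 0.35 | 0.5 | 0.8 | 1.0 |
|---|---|---|---|---|---|---|
| *Unadjusted interval, adjusted p* | | | | | | |
| 0 | 1.6 | 3.8 | 5.1 | 5.2 | 1.8 | 0.2 |
| 0.3 | 3.5 | 5.9 | 11.3 | 9.7 | 2.9 | 0.4 |
| 0.5 | 4.4 | 10.1 | 18.5 | 16.5 | 4.3 | 0.5 |
| 0.7 | 8.3 | 18.9 | 29.6 | 26.0 | 5.2 | 0.4 |
| *Both from one adjusted difference* | | | | | | |
| 0 | 1.3 | 2.6 | 4.3 | 4.2 | 1.3 | 0.2 |
| 0.3 | 1.5 | 2.8 | 5.1 | 3.6 | 1.3 | 0.2 |
| 0.5 | 1.5 | 4.2 | 4.5 | 3.8 | 0.4 | 0.0 |
| 0.7 | 1.8 | 3.2 | 5.0 | 3.2 | 0.1 | 0.0 |

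What remains in the lower block comes from bootstrap versus permutation alone. A normal-theory check (t-test against ANCOVA, 40,000 trials) at r = 0.5 gives 4.4, 10.4, 17.5, 18.2, 4.6 and 0.6% at the same values of d.

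**Step 4: direction of the conflict.** In a normal-theory run at r = 0.5 and d = 0.5, the unadjusted interval excludes 0 in 60.1% of trials, the adjusted test rejects in 72.0%, and they disagree in 18.2%. A small p-value with an interval spanning zero therefore occurs in (18.2 + 72.0 − 60.1)/2 = 15.05% of trials, and the reverse in 18.2 − 15.05 = 3.15%.

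**Step 5: coverage of the 95% bootstrap interval** (4,000 trials, d = 0). With normal scores it is 94.0–94.4% unadjusted and 93.8–94.4% adjusted. With skewed 1–5 scores it is 94.2–94.8% unadjusted and 93.5–94.2% adjusted.

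**The case against.** The strongest reply is that this may be grammar only. The closing phrase could be meant to govern both outputs; if so, no precision is lost and the change merely clarifies. That reading is possible, though the repeated noun phrase does not favour it, and nothing elsewhere settles it. Every figure above is conditional on the literal reading.

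A raw interval beside an adjusted test is also a defensible plan. It keeps the interval centred on the difference between the displayed arm means, which the adjusted interval would not do. That is true, and it is why the raw means should be labelled descriptive.

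The size rests on r, d and ANCOVA, none of which the documents give. This stands. With change from baseline instead, and equal SDs at both times, the variance ratio to the raw difference would be 2(1 − r): 1.4, 1.0 and 0.6 at r = 0.3, 0.5 and 0.7. That is a reason to name the method.

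Adjusted coverage is slightly lower in seven of the eight comparisons and tied in one. The largest gap is under one percentage point.

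Participants may decline questions, so some baseline scores could be missing. A complete-case adjusted interval loses its advantage once the missing fraction reaches r², which is 9% at r = 0.3 and 25% at r = 0.5. The documents give no missingness rate, and the planned p-value already needs the same score.

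Finally, the RCT Self-Report Measures paragraph mentions only two surveys. The earlier Data Collection section lists three, including one at 6 months, and the reimbursement text also counts three, so the planned comparison is not in doubt.

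**Conclusion.** The point holds and is minor. Followed as written, the plan gives each survey measure an interval that leaves out a covariate its own test uses. Nothing is biased or invalid, and the primary analysis is not affected. On the literal reading with ANCOVA, the unadjusted interval is between 0% (r = 0) and 40% (r = 0.7) wider. Conflict between interval and p-value at 40 per arm ranges from 0.2% to about 30% of trials over the r and d considered, against 0–5% when both come from one adjusted difference. If both outputs were meant to be adjusted, the loss is zero and only the wording is at fault. Under either reading the same sentence needs amending.

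**What to change.** Amend the sentence in the Coding paragraph so that, for each measure, one baseline-adjusted 6-month difference (ANCOVA on that measure's baseline score) supplies the point estimate, the 95% bootstrap interval and the permutation p-value. Resample within arm and refit the same model each time. Show raw arm means as descriptive, and state how a missing baseline score is handled, which the planned p-value requires in any case.

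Gender may be added to the model, since the RCT Randomization section says "We will use a blocked randomization design based on gender", but the fix does not depend on it. At r = 0.5, the standard error is multiplied by 1.000 if gender has no effect and by 0.985 if its effect is 0.3 SD.

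The cost is one sentence and a few lines of code, with no new data, visits or participants.
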